9.5.6 Body weight

Body weight data and changes from baseline (Day 1, predose) will be summarized by treatment regimen, and listed. Figures of mean body weight and mean changes from baseline profiles will be presented by treatment regimen over time.

9.5.7 Hepatic Monitoring

If a patient experiences elevated alanine aminotransferase (ALT) $\geq 3 \times$ upper limit of normal (ULN), alkaline phosphatase (ALP) $\geq 2 \times$ ULN, or elevated total bilirubin (TBL) $\geq 2 \times$ ULN, liver tests will be performed to confirm the abnormality.

Additional safety data will be collected if 1 or more of the following conditions occur:

- Elevation of serum ALT to $\geq 5 \times$ ULN on 2 or more consecutive blood tests
- Elevated serum TBL to $\geq 2 \times$ ULN (except for cases of known Gilbert's syndrome)
- Elevation of serum ALP to $\geq 2 \times$ ULN on 2 or more consecutive blood tests
- Patient discontinued from treatment because of a hepatic event or abnormality of liver tests
- Hepatic event considered to be an SAE

The patient's liver disease history and associated person liver disease history data will be listed. Any concomitant medication of acetaminophen/paracetamol will be listed. Results from any hepatic monitoring procedures, such as a magnetic resonance elastography (MRE) scan, and a biopsy assessment will be listed, if performed.

Hepatic risk factor assessment data will be listed. Liver related signs and symptoms data will be summarized by treatment regimen, and listed. Alcohol and recreational drug use data will also be listed.

All hepatic chemistry, hematology, coagulation, and serology data, as well as haptoglobin, will be listed. Values outside the reference ranges will be flagged on the individual patient data listings.

9.5.8 Pancreatic Safety

If a patient experiences elevated serum amylase or lipase values $\geq 3 \times$ ULN, additional monitoring and tests will be performed to confirm the abnormality, even in asymptomatic patients.

All serum amylase and lipase data will be summarized by treatment regimen, and listed.

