- m Patients will be required to fast for at least 8 hours before each blood sample is drawn.
- n These tests will be performed at the local laboratory.
- o These tests will be performed per investigator's discretion.
- p Procedures may be repeated throughout the study as deemed necessary by the investigator.
- q Patients may be required to remain at the CRU longer than the planned discharging day at the investigator's discretion to assure patients' safety or to provide additional safety monitoring.
- r IMP will be administered after an overnight fast of at least 8 hours. IMP must be administered at least 6 days after the previous dose.

- s Assessments of injection-site reactions will be included in the medical assessments.
- t Weight will be measured in a consistent way per Section 9.4.2.1, always predose.
- u OGTT (serum glucose and insulin) sampling schedule: Pre-glucose dose (75 g) and 0.5, 1, 1.5, and 2 hours post glucose dose. Patients should consume the glucose load within 5 minutes after an overnight fast of at least 10 hours.
- v Only insulin and glucagon will be measured at 24 hours postdose on Day 51. All other time points include fasting glucose.
- w Meal intake and subjective rating of appetite sensation will be evaluated before and 4 to 5 hours after standardized lunch and dinner meals on Days -1, 2, and 51. The standardized lunch and dinner meals will be provided at least 4 hours after the previous meal or the ingestion of glucose in the OGTT.
- x Lipid panel includes high-density lipoprotein cholesterol, low-density lipoprotein cholesterol, total cholesterol, and triglycerides. Triglyceride and total cholesterol concentrations in the safety panel will not be required on the days that the lipid panel is performed.
- y Exploratory storage samples may be assayed for biomarkers like adiponectin, cortisol, and bone biomarkers. Refer to Section 9.6.2 for details.

3. Introduction

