5.1. Overall Design

Study GPGC is a Phase 1, multiple-site, patient- and investigator-blind, placebo-controlled, randomized, parallel dose–group, 8-week MAD study in Japanese patients with T2DM.

Study governance considerations are described in detail in [Appendix 3](#).

[Figure GPGC 5.1](#) illustrates the study design.

[figure not shown]

Figure GPGC 5.1. Illustration of study design for Protocol I8F-JE-GPGC.

This study consists of 3 cohorts. Patients will be randomized to 4 treatment groups, including 3 dose levels of LY3298176 and placebo as shown in [Figure GPGC 5.1](#). Patients will be administered 8 weekly SC doses of LY3298176 or placebo. Study procedures and timing for prestudy, treatment, and follow-up phases are outlined in [Section 2](#).

Screening to Prestudy

Patient eligibility for this study will be determined at a screening visit. Eligible patients will visit the clinical research unit (CRU) before Day -1 to receive training on the 7-point self-monitored plasma glucose (SMPG), glucose meters, test strips, and diaries. Patients will conduct the 7-point SMPG until the day before Day -1. In addition, patients treated with metformin or DPP-IV inhibitors (except for omarigliptin, trelagliptin, and linagliptin) will be required to withdraw their treatment and have at least a 28-day washout period before dosing with investigational medicinal product (IMP). These patients will be required to monitor their plasma glucose (PG) levels during the washout period.

Treatment Period

Patients will be admitted to the CRU on Day -1. If the investigator decides not to administer the first dose to a patient on a particular day based on the results of medical assessments, vital signs, or electrocardiograms (ECGs), the patient may be rescheduled to participate in the study, and any procedures performed up to that point may be repeated.

Patients will be given SC doses of LY3298176 (or placebo) on Days 1, 8, 15, 22, 29, 36, 43, and 50 after an overnight fast (at least 8 hours). Even if there are visit allowances of ± 1 day, the interval of each IMP administration must be at least 6 days.

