9.4.4.2. Pancreatic Safety

Serum amylase and lipase measurements will be collected as part of the clinical laboratory testing at time points specified in the Schedule of Activities (Section 2). Additional measurements may be performed at the investigator's discretion. Further diagnostic assessments will be recommended as per the algorithm (refer to [Appendix 6](#)) for the monitoring of pancreatic events whenever lipase and/or amylase is confirmed to be $\geq 3 \times$ ULN at any visit postdose, even if the patient is asymptomatic. If pancreatitis is suspected, the case will be further defined during an adjudication process. Any patient who develops symptoms of pancreatitis must not receive further administration of LY3298176.

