Appendix 2. Clinical Laboratory Tests

Laboratory Tests

Hematology^a	Clinical Chemistry (fasting)^a
Hematocrit	Sodium
Hemoglobin	Potassium
Erythrocyte count (RBC)	Chloride
Mean cell volume	Serum creatinine
Mean cell hemoglobin	Calcium
Mean cell hemoglobin concentration	Phosphorus
Leukocytes (WBC)	Glucose
Platelets	Blood urea nitrogen
Differential WBC Absolute counts of:	Uric acid
Neutrophils	Total protein
Lymphocytes	Albumin
Monocytes	Total bilirubin
Eosinophils	Alkaline phosphatase
Basophils	Alanine aminotransferase
	Aspartate aminotransferase
	Lipase
Urinalysis^a	Amylase
Specific gravity	Total cholesterol ^f
pH	Triglyceride ^f
Protein	eGFR ^e
Glucose	
Ketones	
Bilirubin	
Urobilinogen	
Blood	
Leukocytes	
Microscopy ^b	
Lipid Panel^{c,d}	Biomarkers^d
HDL-C	Fasting plasma glucose, insulin, glucagon ^c
LDL-C (calculated)	OGTT serum glucose and insulin ^c
Total cholesterol	Exploratory storage sample ^c
Triglycerides	
Serology^{a,e}	Other Tests
Hepatitis B surface antigen	Pregnancy test (urine, serum) ^{a,b}
Hepatitis C antibody	Follicle-stimulating hormone ^{a,b,e}
HIV antibody and/or HIV antigen	Drug and alcohol screen ^a
	Hemoglobin A1c ^{c,d}
	Pharmacogenetic sample (storage) ^{c,d}
	Nonpharmacogenetic sampling (storage) ^{c,d}
	LY3298176 Plasma levels ^{d,g}
	Immunogenicity ^{d,g}

Abbreviations: eGFR = estimated glomerular filtrating ratio; HDL-C = high-density lipoprotein cholesterol; HIV = human immunodeficiency virus; LDL-C = low-density lipoprotein cholesterol; OGTT = oral glucose tolerance test; RBC = red blood cells, WBC = white blood cells.

^a Performed at local laboratories.

^b If clinically indicated, per investigator's discretion.

^c Performed or stored at a central laboratory.

- d These results will not be reported to investigator sites except for the screening hemoglobin A1c.
- e Performed at screening only.
- f Total cholesterol and triglyceride concentrations in the safety panel will not be required on the days that the lipid panel is performed.
- g Assayed at Lilly-designated laboratory.

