Appendix 7. Blood Sampling Summary

This table summarizes the approximate number of samples and blood volumes for all blood sampling (screening, safety laboratories, bioanalytical assays, and the other tests) during the study.

Protocol I8F-JE-GPGC Sampling Summary

Purpose	Blood Volume per Sample (mL)	Number of Blood Samples		Total Volume (mL)	
		Cohort 1 or 2	Cohort 3	Cohort 1 or 2	Cohort 3
Screening serology and Serum pregnancy tests ^a	9 ^b	1	1	9	9
Clinical safety laboratory tests ^a	10 ^b	20	16	200	160
Lipid panel	2.5	3	3	7.5	7.5
LY3298176 pharmacokinetics	3	18	18	54	54
Potential additional LY3298176 pharmacokinetic samples	3	3	3	9	9
Glucagon	2	15	13	30	26
Fasting plasma glucose and insulin	4.5	15	13	67.5	58.5
Oral glucose tolerance test (serum glucose and insulin)	2.5	10	10	25	25
HbA1c	2	4	4	8	8
Immunogenicity	6	4	4	24	24
Exploratory storage sample ^d					
Adiponectin	2	2	2	4	4
Cortisol	2.5	3	3	7.5	7.5
Bone biomarkers	3.5	2	2	7	7
Pharmacogenetics	6	1	1	6	6
Nonpharmacogenetics Storage sample	4.5	6	6	27	27
Total				485.5 ^c	432.5 ^c

Abbreviation: HbA1c = hemoglobin A1c.

^a Additional samples may be drawn if needed for safety purposes.

^b Because screening and safety (chemistry and hematology) tests are performed at local laboratories at each site, this volume is an estimate and will vary depending on the local laboratory's testing requirements.

^c The maximum blood volume will increase if follow-up visits for antidrug antibody testing are needed.

^d Blood volumes for this storage sample is calculated based on the assumption that the following biomarkers will be assayed for.

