9.5.3 Clinical laboratory parameters

All clinical chemistry and hematology data will be summarized by treatment regimen and parameter together with changes from baseline, where baseline is defined as Day -1, and listed. Urinalysis data will be listed. Additionally clinical chemistry, hematology, and urinalysis data outside the reference ranges will be listed.

Values for any clinical chemistry, hematology, and urinalysis values outside the reference ranges will be flagged on the individual patient data listings.

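### Amylase, lipase and liver tests come from each site's local laboratory, but the SAP summarises them by regimen without stating any scaling to the local upper limit of normal

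*SAP*

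**What the plan says.** **Where the samples are assayed.** Protocol 5.1 describes the trial: "Study GPGC is a Phase 1, multiple-site, patient- and investigator-blind, placebo-controlled, randomized". Footnote n to the Schedule of Activities (Protocol Section 2), attached to hematology, chemistry and urinalysis, reads "These tests will be performed at the local laboratory". Protocol Appendix 2 places amylase, lipase, ALT, AST, ALP and total bilirubin in the chemistry panel, marked "Performed at local laboratories". A footnote in Appendix 7 explains why blood volumes are only estimates: "Because screening and safety (chemistry and hematology) tests are performed at local laboratories at each site".

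**How the results are summarised.** SAP 9.5.3: "All clinical chemistry and hematology data will be summarized by treatment regimen and parameter together with changes from baseline", with Day -1 as baseline. SAP 9.5.8, for pancreatic enzymes: "All serum amylase and lipase data will be summarized by treatment regimen, and listed". SAP 9.1 gives the statistics: arithmetic mean, SD, median, minimum, maximum and N. Triggered hepatic follow-up tests are handled separately in SAP 9.5.7: "All hepatic chemistry, hematology, coagulation, and serology data, as well as haptoglobin, will be listed".

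**How the plan judges these analytes.** Protocol 9.4.4.2 calls for further work-up "whenever lipase and/or amylase is confirmed to be" at least 3 times ULN. Exclusion criterion 38, Protocol 8.1 and 9.4.4.1, and Appendices 4 and 6 also use multiples of an upper limit for these enzymes and for bilirubin.

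**What happens to reference ranges.** Protocol 10.3.1.2 promises a table of out-of-range laboratory data by parameter and treatment group. SAP 9.5.3 provides flags and a listing only. SAP Section 11 reports no changes from the protocol's analyses.

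**The concern.** Several laboratories may report the same enzyme against different reference limits. The plan allows for this: inclusion criterion 7 accepts the reference range of the investigative site, and the Appendix 4 levels for ALT, AST and bilirubin refer to the laboratory's own upper limit. A regimen mean in reported units would then combine patients whose numbers are not on one scale, and could not be read against the thresholds that the plan uses for the same analytes.

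Two features make this worth settling. Protocol Appendix 6 says that pancreatic enzymes are monitored both to learn their natural variability in type 2 diabetes and to detect an effect of the drug on the exocrine pancreas; a laboratory scale difference would disturb both. The groups are also small: 12, 16 and 12 patients on active drug against 3 + 3 + 3 = 9 on pooled placebo. Protocol 7.2 mentions no stratification of randomization by site, so the laboratory mix of a regimen and of placebo can differ by chance.

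**Working it through.** **Text check.** Neither document expresses these six analytes as multiples of ULN in a summary, harmonises laboratories, puts a site term in a laboratory summary, or counts patients by ULN category. The plan gives no figure of its own on this point, so there is nothing to reproduce.

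**Inputs for the illustration.** The documents give no ULNs, number of sites, site split or assay variability. All of the following are therefore assumptions: two laboratories, patients split 50:50, the same distribution of true values in multiples of ULN at both, and a within-laboratory CV of c = 0.30. Laboratory A has ULN 1 unit and laboratory B has ULN R units. Only the group sizes (12 active, 9 placebo) come from the documents.

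**Pooled CV of values in reported units.** With the true mean at 1 × ULN:

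- mean = (1 + R)/2
- variance = c²(1 + R²)/2 + (R − 1)²/4
- CV = √variance / mean

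| R | c²(1+R²)/2 | (R−1)²/4 | mean | pooled CV |
|---|---|---|---|---|
| 1 | 0.0900 | 0 | 1 | 30% |
| 1.25 | 0.1153 | 0.0156 | 1.125 | 32% |
| 1.5 | 0.1463 | 0.0625 | 1.25 | 37% |
| 2 | 0.2250 | 0.2500 | 1.5 | 46% |

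**Change from baseline.** A rise of 0.5 × ULN is 0.5 units at A and 0.5R units at B: 0.5 against 0.75 for R = 1.5, and 0.5 against 1.0 for R = 2. Subtracting baseline removes an additive laboratory offset but not a proportional difference.

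**Reading a summary against a threshold.** A value equal to 3 × ULN at A is 3/R × ULN at B: 2.4, 2.0 and 1.5 for R = 1.25, 1.5 and 2. A maximum in reported units therefore does not show whether a threshold was crossed.

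**Chance imbalance in laboratory mix, no drug effect.** If a and b are the shares of active and placebo patients at laboratory B, the ratio of expected means is (1 + (R−1)a)/(1 + (R−1)b). For R = 1.5, a = 0.75 and b = 0.50, it is 1.375/1.25 = 1.10. Drawing a from 12 patients and b from 9, each patient at B with probability 0.5 (200,000 draws), gives these 95% ranges:

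- R = 1.25: 0.91 to 1.11
- R = 1.5: 0.84 to 1.20
- R = 2: 0.75 to 1.36

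These ranges reflect laboratory mix only and exclude ordinary variation between patients.

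**The case against.** The strongest reply is that nothing in the trial is decided on these summaries. The pancreatic and hepatic rules apply to individual patients against the ULN, the stopping criteria in Protocol 7.4.1 use events and patient counts, and the laboratory summaries are descriptive in a study not sized for any statistical requirement. All of this stands and limits the point to the quality of the regimen-level description. SAP 9.2 also summarises site ID by regimen, so a gross imbalance in site mix would be visible, although the enzyme tables would not be corrected for it.

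A second reply is that values in reported units are inferred from silence. Table layouts are in a separate shell document that was not available, and no section says that site methods or ranges differ. This also stands. The supportable statement is that the SAP gives no rule, not that scales are known to be mixed.

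A third reply is that the protocol already has a range-based summary, the out-of-range table in 10.3.1.2. But the SAP keeps only the listing. SAP Section 3 says that the SAP supersedes the protocol's statistical considerations and will identify substantial differences, and Section 11 identifies none. This strengthens the case for a change.

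Two stronger readings are tempting. One is that every safety threshold in the plan is a multiple of ULN. That is not so: creatinine, electrolytes, blood counts, QTc, blood pressure and glucose have absolute limits (Protocol 9.4.4.4.1 and Appendix 4). The other is that cohorts enrol strictly in sequence, so that site mix must differ between a regimen and pooled placebo. Under Protocol 5.1, Cohort 3 may start once the initial staggered group of Cohort 2 has been reviewed, so the two can overlap, and each cohort has its own randomized placebo patients. The documents support possible chance imbalance, not a systematic one.

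**Conclusion.** The point holds as a gap in the descriptive safety analysis. Six analytes measured at local laboratories are to be summarised by regimen on an unstated scale, while the plan's thresholds for them are relative to a laboratory upper limit. Under the SAP as written, no ULN-relative summary by regimen remains.

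The size is conditional. With two laboratories at 50:50 and a 30% within-laboratory CV, the pooled CV rises by about 2, 7 and 16 percentage points for ULN ratios of 1.25, 1.5 and 2. If the laboratories share a method and range, the effect is nil.

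A reader might take the laboratory-only CV, (R − 1)/(R + 1), which is 11%, 20% and 33% at these ratios, as the increase in the observed CV. It is not, because it assumes no variation between patients within a laboratory. Nor do the documents support an inference that detection of an abnormal result in an individual patient is impaired: that rests on the ULN rules and flags, which are unaffected.

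**What to change.** 1. In SAP 9.5.3 and 9.5.8, summarise amylase, lipase, ALT, AST, ALP and total bilirubin, and their changes from baseline, as multiples of the reporting laboratory's ULN. Keep reported values and local ranges in the listings.
2. Add a table by regimen counting patients who cross each ULN threshold already in the plan, with the source section named for each row. No new threshold is needed.
3. Restore the out-of-range tabulation by treatment group from Protocol 10.3.1.2, or record its removal in SAP Section 11.

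The cost is one derived variable and a few more tables. Flagging out-of-range results already requires the reference ranges, so no new data are needed. One limit remains: dividing by ULN does not fully harmonise laboratories that define their reference ranges differently, and the SAP should say so beside the tables.

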9.5.9 Hypersensitivity and Injection Site Reactions

Hypersensitivity reaction data will be listed and summarized in frequency tables by treatment regimen, and timepoint.

Injection-site reaction data, including erythema, induration, pain, pruritus, and edema, will also be listed and summarized in frequency tables by treatment regimen, and timepoint.

9.5.10 Glucose Monitoring and Hyperglycemia/Hypoglycemia Reporting

Hypoglycemic events will be appropriately recorded in the CRF. In the case of a hypoglycemic event, the actual blood glucose value, if measured, will be recorded in the CRF, together with any treatments administered. Each category of hypoglycemic event (defined below) will be listed and summarized by treatment regimen.

Blood glucose levels will be listed for individual patients and summarized by treatment regimen.

Hyperglycemia and Hypoglycemia

Hyperglycemic events will be reported by the investigator or designated physician who will be responsible for advising the patient on what further actions to take. Hypoglycemic events will be recorded in the CRF, together with any treatments administered.

The main categories of hypoglycemia are as follows:

- **Documented Glucose Alert Level (Level 1):** plasma/serum glucose ≤ 70 mg/dL (3.9 mmol/L)
 - **Documented symptomatic hypoglycemia:** with typical symptoms of hypoglycemia.
 - **Documented asymptomatic hypoglycemia:** without typical symptoms of hypoglycemia.

- **Documented unspecified hypoglycemia:** with no information about symptoms of hypoglycemia available. (This has also been called unclassifiable hypoglycemia.)
- **Documented Clinically Significant Hypoglycemia (Level 2):** with similar criterion as above except for threshold plasma/serum glucose <54 mg/dL (3.0 mmol/L)
 - **Symptomatic hypoglycemia:** an event during which typical symptoms of hypoglycemia are accompanied by PG <54 mg/dL (3.0 mmol/L)
 - **Asymptomatic hypoglycemia:** an event not accompanied by typical symptoms of hypoglycemia but with PG <54 mg/dL (3.0 mmol/L)
 - **Unspecified hypoglycaemia:** an event during which PG <54 mg/dL (3.0 mmol/L) but no information relative to symptoms of hypoglycemia was recorded
- **Severe Hypoglycemia (Level 3)**
 - **Severe hypoglycemia (in adults):** Patients had altered mental status, and could not assist in their own care, or were semiconscious or unconscious, or experienced coma with or without seizures, and the assistance of another person was to actively administer carbohydrate, glucagon, or other resuscitative actions. Plasma/serum glucose measurements may not be available during such an event, but neurological recovery attributable to the restoration of plasma/serum glucose concentration to normal is considered sufficient evidence that the event was induced by a low plasma/serum concentration (plasma/serum glucose ≤ 70 mg/dL [3.9 mmol/L]).
 - **Severe hypoglycemia requiring medical attention:** Severe hypoglycemic events when patients require therapy by Health Care Providers (Emergency Medical Technicians, emergency room personnel, etc) are of particular interest to payers. Therefore, some clinical trials may collect data on this subset of severe hypoglycemia episodes, especially if economic outcomes analyses may be based on trial results.

- **Other Hypoglycemia**

- **Nocturnal hypoglycemia:** Any documented hypoglycemic event (including severe hypoglycemia) that occurs at night and presumably during sleep. At Lilly, this is captured as hypoglycemia that occurs between bedtime and waking. This definition is more useful than the commonly used ~midnight to ~6 AM definition, which does not take patients' individual sleep times into consideration and is consistent with the American Diabetes Association recommendations for reporting events that occur during sleep (American Diabetes Association 2005). It is also important to collect the actual time when a hypoglycemic event occurred to allow further characterization of hypoglycemia timing (e.g., to allow analysis of frequency of events occurring during a 24-hr time period). Nocturnal hypoglycemia may occur at severity Levels 1, 2, or 3.
- **Relative hypoglycemia (also referred to as pseudohypoglycemia [Seaquist et al. 2013]):** An event during which typical symptoms of hypoglycemia occur, that does not require the assistance of another person, and is accompanied by plasma/serum glucose >70 mg/dL (3.9 mmol/L). The plasma/serum glucose value for patients with chronically poor glycemic control can decrease so rapidly that patients may report symptoms of hypoglycemia before their plasma/serum glucose concentration falls below 70 mg/dL (3.9 mmol/L). Events with plasma/serum glucose ≤ 70 mg/dL should not be categorized as relative hypoglycemia. Evaluation and statistical analysis of this category is optional. However, if a patient reports a relative hypoglycemia event where assistance from another person was received or the patient experienced significant symptoms, the study team should clarify the circumstances to ensure the event is not a severe hypoglycemia event and report it appropriately.
- **Probable symptomatic hypoglycemia:** Symptoms of hypoglycemia were present, but plasma/serum glucose measurement was not reported.
- **Overall (or total) hypoglycemia:** This optional category combines most cases of hypoglycemia (documented hypoglycemia and probable symptomatic hypoglycemia, including severe hypoglycemia). It does not include relative hypoglycemia. Nocturnal and severe hypoglycemia are special cases of documented or probable hypoglycemia. If an event of hypoglycemia falls into multiple subcategories, that event should only be counted once in the category of overall (or total) hypoglycemia.

